1.1 Delineamento do estudo

1.2 This is a randomized clinical trial aimed at comparing the effects of cryotherapy and low-level laser therapy on postpartum women up to 24 hours after delivery. The control group will receive cryotherapy (CG), and the intervention group will receive low-level laser therapy (GL). This study was randomized by drawing lots, where there was a paper in a black bag with "LLT" or "cryotherapy" written on it, and the patient would draw the paper from the bag to select the treatment to be applied. A randomized clinical trial is the gold standard for an experimental study or clinical trial, allowing the evaluation and demonstration of cause-and-effect relationships between various independent and dependent variables (SHARMA; SRIVASTAV; SAMUEL, 2020). Randomization by randomly generated numbers by computer, tables, coin toss,

and dice games is considered appropriate (SOUZA; SOUSA; SANTOS JR. et al, 2019).

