1.3 Location and Condict of the Study

The present study was conducted and validated at the Municipal Hospital of Novo Hamburgo, with application carried out by the researcher.

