The two most common means of LLLT application are characterized by a wavelength of approximately 633 nm (red light) and 904 nm (infrared), capable of inducing mitochondrial activity and initiating reactions at the cellular membrane level, respectively. (KITCHEN, 2003).

Patients underwent evaluation using a questionnaire, the Patient Assessment Form, developed by the researcher. Pain and edema were evaluated using the Visual Analog Scale (VAS), McGill Pain Questionnaire (MPQ), and REEDA scale before, immediately after, and 24 hours after therapy application.

Pain was assessed on a scale of 0 to 10 using the VAS, with 0 indicating no pain and 10 indicating maximum pain intensity.

The McGill Pain Questionnaire (MPQ) was used to assess other characteristics of pain, not just intensity. This questionnaire captures quantitative measures of pain, with established validity and reliability, allowing for discrimination of various pain components. The questionnaire consists of 20 items, or groups, with each group containing several words from which the patient selects the one that best identifies their pain, selecting only one word per group. The groups are subdivided into sensory responses to painful experience (Groups 1-10), affective responses (Groups 11-15), evaluative responses (Group 16), and miscellaneous

(Groups 17-20). The questionnaire takes 3 to 4 minutes to complete. (PIMENTA; TEIXEIRA, 1996).

Edema was evaluated using the REEDA scale, which assesses inflammatory processes and tissue recovery following perineal trauma. Five scar healing items are evaluated: redness, swelling, bruising, discharge, and wound edge approximation (coaptation). A score of zero to three is assigned to each item evaluated by the assessing professional, with a maximum score of 15 indicating the worst perineal healing. (ALVARENGA et al., 2015).

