2 DATA COLLECTION PROTOCOL

Step 1: Contact and presentation to the head responsible of the Obstetrics Center and then to the coordinating nurse of the Obstetrics department at the Municipal Hospital of Novo Hamburgo. After introducing myself and presenting the project, I provided my contact information and made myself available to be called whenever there was a patient who fit the sample profile of this study, taking responsibility for its implementation.

Step 2: After signing the Informed Consent Form (ICF), a physiotherapeutic assessment was conducted with the patient, as per the form in Appendix B.

Step 3: The patient underwent random selection to determine which intervention group she would be assigned to.

Step 4: After group assignment, within 12 hours post-vaginal delivery, the patient underwent an assessment of edema and pain using available scales (Appendices A, B, and C).

Step 5: The randomly determined intervention, either cryotherapy or laser therapy, was administered within 12 hours post-immediate vaginal delivery.

Following the application described in this study, the patient was immediately reassessed for pain using the VAS scale.

Step 6: The patient was reassessed 24 hours post-delivery, and pain and edema scales were applied. After this period, the patient was discharged.

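### The step order takes the baseline pain and edema scales after the woman has drawn her treatment, so baseline scores can be influenced by knowledge of the group.

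*Combined protocol and SAP*

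**What the plan says.** Section 1.2 describes allocation by lots. Slips naming one of the two treatments are in a black bag, and "the patient would draw the paper from the bag to select the treatment to be applied". Section 1.3 says that the study took place at one hospital, "with application carried out by the researcher".

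Section 2 sets the order of events:

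- At Step 1 the researcher "made myself available to be called whenever there was a patient who fit the sample profile of this study".
- Step 2 covers consent and then a physiotherapy evaluation, for which the text cites Appendix B.
- Step 3 is the draw that decides the group.
- Step 4 is where the baseline scales are taken: "After group assignment, within 12 hours post-vaginal delivery, the patient underwent an assessment of edema and pain using available scales". Three appendices, A to C, are cited for them.
- At Step 5 the treatment is given as drawn: "The randomly determined intervention, either cryotherapy or laser therapy, was administered". Pain is then scored again by VAS straight afterwards.
- At Step 6 pain and edema are scored again at 24 hours.

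Section 1.9 says that VAS, McGill and REEDA were taken before therapy and twice after it. For REEDA, "A score of zero to three is assigned to each item evaluated by the assessing professional". The documents describe no blinding, number of slips, replacement rule or record of draws. They state no sample size, SD or analysis model.

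**The concern.** A baseline score is useful in a randomized comparison because allocation cannot have affected it. Here the woman draws the slip herself and then rates her pain. VAS and McGill are self-reported, REEDA is a rater's judgement, and ice and laser are easy to tell apart. If hoping for one treatment, or being disappointed with the other, changes what is reported before treatment, the arms differ at baseline for a reason other than chance. Any analysis that uses baseline then takes in part or all of that difference.

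A lesser matter is that, as the draw is described, a reader cannot check that the drawn slip was always the one followed.

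**Working it through.** **1. Order of events.** Section 2 numbers the draw 3, the scales 4 and the treatment 5, and Step 4 says outright that it follows assignment. Section 1.9 places the first scales before therapy. That agrees with Step 4 and does not move them ahead of the draw.

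**2. Could Step 2 hold an earlier baseline?** Step 2 precedes the draw and cites Appendix B, and Step 4 also cites Appendix B. Section 1.4 and the printed form label the physiotherapeutic assessment Appendix A, and that form has no pain or edema scale. The reference at Step 2 therefore looks like a labelling slip. Appendices B and C are not in the text available, so scores taken before the draw cannot be ruled out.

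**3. Size of the effect.** There is no figure in the plan to reproduce. Assumed inputs: VAS SD 2 at each time, correlation ρ = 0.5 between baseline and later score, n = 20 per arm, no true treatment difference. Knowing the group shifts reported pain in one arm by δ = 0.5 or 1 point, either at baseline only or equally at baseline and follow-up.

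Expected bias (absolute size):

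| Analysis | Baseline only | Persisting |
|---|---|---|
| Change from baseline | δ = 0.5 or 1 | δ − δ = 0 |
| Baseline-adjusted | ρδ = 0.25 or 0.5 | (1 − ρ)δ = 0.25 or 0.5 |
| Later score alone | 0 | δ = 0.5 or 1 |

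The two baseline-adjusted biases have opposite signs.

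Standard errors:

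- Later score: 2 × √(2/20) = 0.63.
- Change: 2 × √(2(1 − 0.5)) × √(2/20) = 0.63.

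For the full bias, the ratio to its standard error is 0.5/0.63 = 0.79 or 1/0.63 = 1.58. With a two-sided 5% t test on 38 degrees of freedom, the false-positive rate is 12% or 34%. That applies to change under a baseline-only shift and to the later score under a persisting shift. The unbiased analysis stays at 5% in each case. Simulation puts the baseline-adjusted analysis at about 7% (δ = 0.5) and 13% to 14% (δ = 1) in both cases.

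**4. Can the two analyses reveal the shift?** With no shift, the difference between the unadjusted and adjusted estimates still varies, because baseline differs by chance. Simulated on the same assumptions, its SD is 0.33, and it is at least 0.25 point in about 40% of trials and at least 0.5 in about 12%. A real 0.5-point shift moves its expected value by ρδ = 0.25, less than one SD.

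**5. The draw record.** Suppose, for illustration only, that 1 in 5 laser slips drawn by women with episiotomy were redrawn once from a 50:50 bag. Then P(laser given episiotomy) = 0.5 − 0.25 × 0.2 = 0.45 against 0.50 for the others, a 5-point gap. If episiotomy changed mean VAS by an assumed 1 to 2 points, the contrast would move by 0.05 to 0.1 point.

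**The case against.** The strongest objection is that the bias calculation depends on where the shift occurs. Women and the researcher know the group at every later score too. A baseline-only shift is thus one scenario among several, and the ranking of the analyses reverses if the shift persists. This stands. A reader might infer that change from baseline should be avoided in general, but the documents do not support that. They state no analysis, and change is the unbiased choice under a persisting shift. A reader might also take a marked gap between adjusted and unadjusted results as proof of contaminated baselines. Clean trials produce such gaps too often for that.

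The second objection is that drawing lots is a valid chance method and that section 1.2 itself accepts coin toss and dice. This also stands. A reader might infer from the missing slip count and log that draws were repeated or disregarded. Nothing in the documents suggests it, Step 5 says that the drawn treatment was given, and a log that is not described may still exist. The gap is missing detail, not evidence of failed randomization. Nor do the documents make stratified blocks in envelopes necessary. Someone tracking a stratum could guess about 64% to 66% of assignments with blocks of 6, 8 and 10, against 57% to 62% for a bag of equal slips not replaced (N = 20 to 60).

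Neither objection touches the order of Steps 3 and 4.

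**Conclusion.** The point holds, centred on the step order. Followed as written, the plan takes subjective baseline scores when the woman already knows her treatment, with no blinding described for the rater. The bias may be nil. Under the assumed SD, correlation and arm size, a shift of 0.5 to 1 VAS point could bias an analysis by 0 to 1 point, with false-positive rates from 5% to 34%. Which analysis is affected depends on whether the shift persists. Since N, SD, correlation and the shift are all assumed, these figures show how the problem works and do not estimate its size in this trial. The missing record of draws is secondary: it limits what readers can verify. Confidence is medium, because Appendices B and C could show scores taken before the draw.

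**What to change.** For any woman still to be recruited:

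- Record eligibility and trauma type, then take the Step 4 scales, and only then make the Step 3 draw.
- Log each draw with study number, time and slip drawn.

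The cost is a reordering of steps and one log sheet. Stratified blocks in sealed envelopes are optional.

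If recruitment is complete, as the past tense suggests:

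- State as a limitation that baseline scores followed assignment.
- Report any pain or edema scores recorded before the draw, the slip counts, the replacement rule and any redraws.
- Present the comparison of later scores both with and without adjustment for baseline, as a sensitivity analysis and not as a test for contamination.

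This needs no new patient data. Leaving out baseline costs some precision: the standard error is about 0.63 instead of 0.57 VAS point under the same assumptions. Neither analysis removes bias from later scores that are themselves given with the group known, so that should be said alongside the results.

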1.3 Location and Condict of the Study

The present study was conducted and validated at the Municipal Hospital of Novo Hamburgo, with application carried out by the researcher.

1.4 Data Collection

The data collection was performed through Physiotherapeutic Assessment (APPENDIX A), and the data were stored in an Excel spreadsheet. **Amostragem e amostra**

1.4.1 Sampling

1.4.2 Patients in immediate postpartum vaginal who meet the inclusion criteria.

1.4.3 Sample

1.5 The sample consisted of women admitted to a public hospital in the Vale do Sinos region who underwent vaginal delivery and experienced some complication during delivery, such as episiotomy or first- or second-degree laceration. The sample size calculation was based on studies by Santos et al. (2012) and Morais et al. (2016), using the StatCalc – Sample Size and Power tool in the Epilnfo software.

1.6 Inclusion and Exclusion Criteria

1.6.1 Inclusion Criteria

- a) Patients who underwent vaginal delivery;
- b) Experienced first- or second-degree laceration;
- c) Underwent episiotomy;
- d) Aged 18 years or older.

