1.6.1 Exclusion Criteria

- a) Patients who underwent cesarean section;
- b) Presented with gestational diabetes;
- c) With HELLP syndrome;
- d) Experienced immediate postpartum hemorrhage;
- e) Had unstable vital signs in immediate postpartum;
- f) Under 18 years old.

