1.7.2 Main Outcome

The idea of using non-pharmacological techniques in immediate postpartum is to reduce pain, edema, and inflammatory processes, causing greater comfort and better recovery in the puerperium.

a) Primary Outcome

- Compare the two techniques to assess which is more effective in relieving pain and/or edema in immediate postpartum up to 12 hours.

b) Secondary Outcome

- Reduce pain and/or edema and promote healing in immediate postpartum.

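### Entry requires perineal trauma but no pain or swelling, and the scales come after the draw, so women already at zero can be randomised into a comparison of relief

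*Combined protocol and SAP*

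**What the plan says.** **Entry.** Section 1.6.1 (Inclusion Criteria) lists four items: "Patients who underwent vaginal delivery", "Experienced first- or second-degree laceration", "Underwent episiotomy" and "Aged 18 years or older". Section 1.4.3 (Sample) shows that laceration and episiotomy are alternatives. The exclusions are cesarean section, gestational diabetes, HELLP syndrome, hemorrhage, unstable vital signs and age under 18. None of these concerns pain or swelling.

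**Outcome.** Section 1.7.2 (Main Outcome) asks which technique is "more effective in relieving pain and/or edema in immediate postpartum up to 12 hours".

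**Scales.** Section 1.9 (Research Instrument) scores the VAS from 0 to 10, "with 0 indicating no pain and 10 indicating maximum pain intensity". Each of the five REEDA items, swelling among them, runs from 0 to 3.

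**Order of steps.** In Section 2 (Data Collection Protocol), consent and the physiotherapeutic form are Step 2 and the draw is Step 3. At Step 4, once the group is assigned, "the patient underwent an assessment of edema and pain using available scales". Treatment follows at Step 5, with an immediate VAS, and the scales are repeated at Step 6.

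**The concern.** The trial asks about relief, but entry does not require anything to relieve. A woman with a small first-degree tear and no pain is eligible. There is an upper limit of 12 hours on time since delivery but no lower one. The Appendix A form records medication used after delivery, yet prior analgesia is not an exclusion. Zero scores are therefore plausible. Because scoring is described only after the draw, a zero cannot keep a woman out.

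On the scale where she scores zero, a woman can only stay the same or worsen, whichever technique she draws. Each such woman pulls the difference between arms in immediate change towards zero. The trial then becomes less able to separate two techniques that differ in women with symptoms. The documents contain no analysis plan, so baseline adjustment cannot be presumed.

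**Working it through.** **Inputs.** The plan has no figure to reproduce. Section 1.4.3 names two cited studies and a software tool, but gives no sample size, effect size, SD, alpha or power. The share f at zero is not given either. Everything below is therefore illustrative.

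**Step 1: dilution.** Let the mean immediate change in symptomatic women be μ₁ in one arm and μ₂ in the other. Let women at zero have the same mean change c in both arms (c = 0 if they stay at zero). The arm means are (1 − f)μ₁ + fc and (1 − f)μ₂ + fc, so

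difference = (1 − f)(μ₁ − μ₂).

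**Step 2: sample size.** For two means, n per arm is proportional to SD²/difference². With the SD held constant, n rises by 1/(1 − f)².

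| f | Difference retained | Sample multiplier |
|---|---|---|
| 5% | 0.95 | 1/0.95² = 1.11 |
| 10% | 0.90 | 1/0.90² = 1.23 |
| 20% | 0.80 | 1/0.80² = 1.56 |
| 30% | 0.70 | 1/0.70² = 2.04 |

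**Step 3: power, on assumed inputs.** Take a difference of 1.5 VAS points in symptomatic women, SD 2.0, two-sided alpha 0.05 and 1:1 allocation. Then 28 per arm gives 80% power when f = 0. Model A keeps the SD at 2.0. Model B uses the variance of a mixture: women at zero have change 0, and the others improve by an assumed 2 points in one arm and 3.5 in the other. Its variance in each arm is (1 − f)SD² + f(1 − f)m², with m = 2 or 3.5, averaged over the two arms.

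| f | Power at 28 per arm, A | Power at 28 per arm, B | n per arm for 80%, A | n per arm for 80%, B |
|---|---|---|---|---|
| 10% | 71% | 68% | 35 | 38 |
| 20% | 61% | 56% | 44 | 50 |
| 30% | 50% | 46% | 57 | 65 |

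Results were similar for a difference of 1.0 with SD 2.0 and for 2.0 with SD 2.5.

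**Step 4: what restricting the comparison recovers.** If women at zero are enrolled but the comparison is made only in those above zero, enrolment must supply 28 symptomatic women per arm: 28/0.9 = 31.1 (32), 28/0.8 = 35 and 28/0.7 = 40. The multiplier falls from 1/(1 − f)² to 1/(1 − f), that is 1.11, 1.25 and 1.43.

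**Limits.** Step 1 fits immediate change on one scale. It applies to swelling in the same way, with its own f, provided REEDA is scored immediately after treatment. Section 1.9 says so, but Step 5 names only the VAS.

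**The case against.** The case on the other side is substantial, and much of it stands.

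- **Women at zero are permitted, not reported.** A reader might infer that they were enrolled and did dilute the result. The documents do not say so. Every participant has perineal trauma, which itself selects for symptoms, and f could be close to zero.
- **No shortfall in sample size can be shown.** If the two cited studies also enrolled without a symptom threshold, their effect size may already include women at the floor, and the multiplier would not apply. The inputs are not stated, so this cannot be settled.
- **These women are not uninformative.** A reader might infer that they carry no information. The outcome is pain and/or edema, so a woman with VAS 0 may have swelling. Her pain may also rise by 24 hours, and a smaller rise in one arm would be a real difference.
- **Nobody is counted as a treatment failure.** That reading is tempting for a woman whose pain rises from zero, but the documents define neither response nor failure.
- **A VAS-only entry rule would be wrong.** It would exclude women with swelling but no pain, although edema is part of the primary outcome.
- **A threshold just above zero does not remove the floor effect.** A woman at VAS 1 can improve by at most 1 point.
- **The order of scoring is not beyond doubt.** Step 2 cites Appendix B and Step 4 cites Appendices A, B and C, while Section 1.4 assigns the physiotherapeutic form to Appendix A. Appendices B and C are not in the text reviewed. However, the Appendix A form has no pain or edema item, and only Step 4 describes scoring before treatment.

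Taking all women with perineal trauma is a defensible broad population. It does not answer the point that relief cannot be observed on a scale already at zero, or that the plan makes no allowance for this.

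**Conclusion.** The point holds as a loss of sensitivity. No criterion requires pain or swelling, the scales bottom out at zero, and scoring is described after the draw. A woman at zero can be randomised and cannot show improvement from baseline on that scale.

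The size depends on f, which is an assumption. The loss is slight at 5% (1.11 times the sample) and material at 20% or 30% (1.56 and 2.04 times). These figures hold for immediate change on a single scale, with constant SD and an effect size that refers to symptomatic women.

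A reader might infer a bias in favour of one technique, but the entry rule supports no such reading, because it applies equally to both arms. Nor do the documents show that the trial is underpowered. The change is worth making because it is cheap and also places baseline scoring before the arm is known.

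**What to change.** **If enrolment can still be changed**
1. Record VAS and REEDA at Step 2, after consent and before the draw.
2. Require for entry a pre-draw score above zero on the VAS or on the REEDA swelling item, rather than on the VAS alone.
3. Compare pain relief in women with pre-draw VAS above zero, and edema relief in women with pre-draw swelling above zero, each adjusted for the baseline score.
4. State in the sample size section what share is expected in each comparison. If the investigators prefer no minimum, they should justify that and allow for f.

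**If enrolment is complete**
1. Report the number at zero on each scale by arm.
2. Adjust for the Step 4 baseline and run each comparison in women above zero.
3. Note that this baseline was scored after allocation. The woman draws the slip herself, so her score may reflect knowledge of her arm.

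**Cost.** No new instrument is needed: one entry line is added and existing scales are moved earlier. Recruitment is slightly slower, the results apply to symptomatic women, and each symptom-specific comparison has fewer women than were randomised.

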1.6.1 Exclusion Criteria

- a) Patients who underwent cesarean section;
- b) Presented with gestational diabetes;
- c) With HELLP syndrome;
- d) Experienced immediate postpartum hemorrhage;
- e) Had unstable vital signs in immediate postpartum;
- f) Under 18 years old.

1.7 Operational Definition of Variables

1.8 1.7.1 Study Factor

The comparison of two non-pharmacological techniques used for pain and edema relief, performed in immediate postpartum up to 12 hours, being evaluated

before the application of the techniques, immediately after, and reevaluated after 24 hours.

1.7.2 Main Outcome

The idea of using non-pharmacological techniques in immediate postpartum is to reduce pain, edema, and inflammatory processes, causing greater comfort and better recovery in the puerperium.

a) Primary Outcome

- Compare the two techniques to assess which is more effective in relieving pain and/or edema in immediate postpartum up to 12 hours.

b) Secondary Outcome

- Reduce pain and/or edema and promote healing in immediate postpartum.

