1.9 Research Instrument

Cryotherapy was performed using a glove containing crushed ice applied to the perineal region for 20 minutes, initiated up to 12 hours postpartum. Patients were assessed before application, immediately after application, and again 24 hours after application. A glove containing crushed ice was chosen due to its anatomical fit and ability to cover the entire perineal region. Francisco et al. (2013) suggest that surface ice has the ability to decrease skin and intramuscular tissue temperature. Compared to other cryotherapy techniques such as gel and frozen pea bags, the ice bag is the most adopted technique for perineal pain relief. The application time aligns with the study by Beleza et al. (2016), indicating that 20

minutes is sufficient time to cause reduction and relief of pain in study participants.

Low-Level Laser Therapy (LLLT), like cryotherapy, was applied up to 12 hours postpartum, targeting the lesion area. Red light radiation was applied at 3 joules, punctually, with a non-contact technique, maintaining a 2 cm distance between points. Subsequently, infrared laser was applied using the conventional contact technique around the lesion extension, punctually, at 6 joules, also maintaining a 2 cm distance between points.

The LLLT device used was the DMC Therapy EC, portable, with a li-ion battery. The red laser had a wavelength of 660nm (\pm 10 nm) and an emitter power of 100 mW (\pm 20%). The infrared laser had a wavelength of 808 nm (\pm 10) and an emitter power of 100 mW (\pm 20%).

The use of infrared radiation is associated with being a superficial thermal agent, used to reduce pain and stiffness, favoring the regeneration of soft tissue injuries and skin problems. (KITCHEN; PARTIDGE, 1991; MICHLOVITZ, 1986).

LLLT application should be punctual, applying firm pressure to the tissue area to be treated, resulting in higher levels of tissue light flow. This application is characterized by the conventional contact technique, whereas the non-contact technique involves application around the wound margins. These combined techniques ensure better application and absorption of radiation. Application should occur around the circumference of the lesion, approximately 1-2 cm from its margins, with application points spaced 2-3 cm apart. (KITCHEN, 2003).

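### The primary question on pain and/or edema names no scale, score or visit and gives no rule for declaring a winner, so an either-wins claim is permitted and a split result cannot be resolved

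*Combined protocol and SAP*

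**What the plan says.** Section 1.7.2 of the combined protocol and SAP gives the primary outcome as "Compare the two techniques to assess which is more effective in relieving pain and/or edema in immediate postpartum up to 12 hours". The secondary outcome is "Reduce pain and/or edema and promote healing in immediate postpartum". It reuses the same pair of constructs and adds healing, so it does not separate primary from secondary measures.

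Section 1.9 (Research Instrument) names two pain instruments, the VAS (0 to 10) and the McGill Pain Questionnaire (MPQ), and one further scale, REEDA. It has all three applied at the same times: "REEDA scale before, immediately after, and 24 hours after therapy application". Section 2 (Data Collection Protocol) differs. Step 5 mentions only the VAS straight after treatment. Step 6 applies unspecified pain and edema scales 24 hours after delivery, whereas Section 1.9 counts from treatment: "Patients were assessed before application, immediately after application, and again 24 hours after application".

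For edema, Section 1.9 says "Edema was evaluated using the REEDA scale". It then describes five items scored 0 to 3, of which swelling is one, and a total "with a maximum score of 15 indicating the worst perineal healing".

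The sample section does not reveal the intended primary endpoint. It says "The sample size calculation was based on studies by" two cited authors' groups and names a software tool, but gives no endpoint, alpha, power or number of patients. The available text has no analysis section, multiplicity rule or rule for discordant results.

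**The concern.** The trial is meant to say which of two techniques is better. With two constructs joined by and/or, several scales and visits, and no decision rule, an analyst who follows the text could declare a winner on whichever comparison reaches significance. The false-positive rate of that claim would be uncontrolled, and a reader could not tell whether the deciding endpoint had been fixed before the results were known.

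The opposite difficulty is a split result. If the laser does better on pain and cryotherapy on edema, or the reverse, the plan asks for a single verdict and gives no means of reaching one.

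The edema measure adds a further choice, because the REEDA swelling item and the REEDA total could point in different directions.

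**Working it through.** **No stated figure to reproduce.** The plan gives no alpha, power or sample size, so the figures below are illustrative.

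**Step 1: does the time phrase settle the endpoint?** Section 1.7.2 ends with a limit of 12 hours. Under Study Factor in Section 1.7 the same limit is attached to giving the techniques: "performed in immediate postpartum up to 12 hours, being evaluated". Section 1.9 and Step 5 also use it as the treatment window, so it most naturally describes treatment and not a visit. If it is read as the outcome time anyway, neither version of the 24-hour visit qualifies and only the immediate assessment remains:
- Step 5: one comparison (VAS), with edema unmeasured.
- Section 1.9: three comparisons (VAS, MPQ, REEDA).

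**Step 2: count the comparisons otherwise**, at one score per scale.
- Section 2: immediate VAS, plus VAS, MPQ and REEDA at 24 hours (taking Step 6 to mean the scales of Section 1.9): 1 + 3 = 4.
- Section 1.9: 3 scales × 2 post-treatment visits = 6.
- Minimum that covers both constructs: one pain and one edema measure = 2.

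**Step 3: chance of at least one false winner under an either-wins reading.** Assumptions: two-sided 0.05 per test, no true difference on any measure.
- Independent tests: 1 − 0.95^k. This gives 1 − 0.95² = 0.0975, 1 − 0.95³ = 0.1426, 1 − 0.95⁴ = 0.1855 and 1 − 0.95⁶ = 0.2649.
- Correlated tests: P(at least one |Z| > 1.960) for multivariate normal Z. Equal correlation 0.9 was obtained by numerical integration. The structured case (0.7 within a construct, 0.2 between) used 2,000,000 simulated draws.

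| Tests (pain + edema) | Independent | Correlation 0.9 | Structured |
|---|---|---|---|
| 2 (1 + 1) | 9.8% | 7.0% | 9.7% |
| 3 (2 + 1) | 14.3% | 8.4% | 12.7% |
| 4 (3 + 1) | 18.5% | 9.4% | 15.2% |
| 6 (4 + 2) | 26.5% | 10.8% | 20.0% |

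A single test stays at 5%.

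**Step 4: both-must-win reading**, one measure per construct, each at 0.05. With both nulls true and independent tests, the chance that both are significant is 0.05 × 0.05 = 0.0025. Simulation gives 0.2% to 0.9% for correlations 0 to 0.5. If one effect is real and very large, the rate rises to about 5% but no further.

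**Step 5: cost of controlling error with two measures**, taking an assumed 80% power per construct at 0.05.
- Fixed split at 0.025: power = Φ(1.960 + 0.842 − 2.241) = Φ(0.561) = 0.71. Restoring 80% needs ((2.241 + 0.842)/(1.960 + 0.842))² = 1.21 times the patients.
- Holm (4,000,000 draws): power per construct 0.775 at correlation 0 and 0.764 at 0.5 if both effects are real; about 0.71 if only one is.
- Both must win, independent tests: 0.80 × 0.80 = 0.64 to declare a winner.

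**The case against.** The strongest reply is that Section 1.7.2 states an objective and not a success criterion. A reader might infer that the plan commits to declaring a winner from either construct. It does not: that rule appears nowhere, and and/or equally admits a requirement to win on both, which Step 4 shows does not inflate error. This stands. What remains is that the text does not choose between the readings. The both-must-win reading is also protected only once one measure per construct has been named, which the plan does not do.

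A reader might also take 26.5%, over five times the assumed level, as the size of the problem. That needs six mutually independent comparisons, although they include repeated scales in the same women. Section 1.9 brings in the MPQ to describe aspects of pain beyond intensity, and Step 5 uses only the VAS, so the smaller counts are more credible. That objection stands too, and the structured figures are the ones to use.

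Finally, because much of the conduct is written in the past tense, a reader might infer that the endpoint was picked after the results were seen. The documents do not show this. They only leave it impossible to exclude.

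The 12-hour phrase is not a good defence. Taken as the outcome time, it leaves either three unranked comparisons or one that omits edema.

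**Conclusion.** The concern holds as a missing decision rule. The primary question covers two constructs without a designated scale, score or visit, and it cannot give a single answer if they disagree. If an either-wins claim were made, the false-winner risk would be about 10% for two tests, 13% for three, 15% for four and 20% for six, under the assumed 0.05 level and structured correlations. Across correlations 0 to 0.9 the range is 7% to 10% for two tests and 11% to 26% for six, the top requiring implausible independence. There is no inflation if both constructs must win on one measure each, or if the immediate VAS is the only test, though the latter drops edema from the stated objective. These figures show direction and range; they correct no figure in the plan. The lack of a rule for discordant results does not depend on any of these assumptions.

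**What to change.** First, disclose whether outcome data had been seen when the primary endpoint was fixed, and label the choice post hoc if so.

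Then replace and/or in Section 1.7.2 with one of the following:

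- **(a) A single primary endpoint** with scale, visit and summary measure, for example the between-arm difference in VAS immediately after application, adjusted for baseline VAS, with everything else secondary. The VAS is the only immediate measure on which Section 1.9 and Step 5 agree. Cost: the primary objective narrows to one construct.
- **(b) One pain and one edema measure, each at one time, in a fixed sequence at 0.05.** Cost: no alpha is split, but the second construct cannot be tested if the first fails.
- **(c) The same two measures as alternative primaries**, with Holm or 0.025 each. Cost: an assumed 80% power per construct falls to about 71% (fixed split, or Holm with only one real effect) or 76% to 78% (Holm, both effects real).
- **(d) Both measures required to win.** Cost: lower power to declare a winner, 64% in the independent case above.

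Under (b) and (c), draw a separate conclusion for each construct. In every case, declare no overall winner if the results are discordant. State whether edema is the REEDA swelling item (0 to 3) or the total (0 to 15). Reconcile Study Factor in Section 1.7, Section 1.9 and Steps 4 to 6 on which scales are taken at the chosen visit and from what moment its timing runs.

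These are text changes that need no new data collection. If the data have already been seen, they cannot make the choice prespecified.
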